3.3.1 Inclusion Criteria

1. Signed Written Informed Consent

- a) Subject is, in the investigator's opinion, willing and able to comply with the protocol requirements.
- b) Subject has given voluntary written informed consent before performance of any study related procedure not part of normal medical care, with the understanding that consent may be withdrawn by the subject at any time without prejudice to their future medical care.

2. Target Population

- a) Eastern Cooperative Oncology Group (ECOG) performance status ≤ 2 .
- b) Life-expectancy > 3 months.
- c) Newly diagnosed, untreated, symptomatic, documented myeloma AND;
 - i) Who are not candidates for high-dose therapy plus SCT because of age (≥ 65 years) or coexisting conditions. Refusal to undergo high dose therapy with SCT is **NOT** sufficient for entry onto CA204116 for a subject < 65 years old. There must be a comorbidity that prevents SCT for a subject < 65 years old, AND;
 - ii) Measureable disease (patient must meet one of these criteria)
 - (a) serum IgG M-protein ≥ 0.5 g/dL OR
 - (b) serum IgA M-protein ≥ 0.5 g/dL OR
 - (c) serum IgM M-protein ≥ 0.5 g/dL OR
 - (d) Urine M-protein ≥ 200 mg/24-hour OR
 - (e) Serum free light chain (sFLC) assay showing involved FLC level ≥ 10 mg/dL (≥ 100 mg/l) provided the serum FLC ratio is abnormal
- d) Subject Re-enrollment: This study does not permit the re-enrollment of a subject that has discontinued the study as a pre-treatment failure.

3. Age and Reproductive Status

- a) Males and Females, ages ≥ 20 years, inclusive
- b) Subjects must be willing to refrain from blood donations during study drug therapy and for 90 days after therapy.
- c) Women of childbearing potential (WOCBP) and men must be using 2 acceptable methods of contraception to avoid pregnancy throughout the study for a period of at least 1 month (4 weeks) before study treatment and women for up to 120 days, men for up to 180 days after the last dose of study drug in such a manner that the risk of pregnancy is minimized. See [Section 3.3.3](#) for the definition of WOCBP and also refer to the Revlimid risk management plan guidelines.

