- d) Women of childbearing potential (WOCBP) must have a negative serum or urine pregnancy test (minimum sensitivity 25 IU/L or equivalent units of HCG) The first should be performed within 10 - 14 days and the second within 24 hours prior to the start of study drug. A prescription for lenalidomide for a female of childbearing potential must not be issued by the prescriber until negative pregnancy tests have been verified by the prescriber.
- e) Women must not be breastfeeding.
- f) WOCBP must agree to follow instructions for method(s) of contraception for the duration of treatment with study drug (s), elotuzumab in combination with lenalidomide/dexamethasone, plus the time to washout (90 days) plus 30 days (duration of ovulatory cycle) for a total of 120 days post-treatment completion.
- g) Males who are sexually active with WOCBP must agree to follow instructions for method(s) of contraception for the duration of treatment with study drug (s), elotuzumab in combination with lenalidomide/dexamethasone, plus the time to washout (90 days) plus 90 days (duration of sperm turnover) for a total of 180 days post-treatment completion.
- h) Azoospermic males and WOCBP who are continuously not heterosexually active are exempt from contraceptive requirements. However they must still undergo pregnancy testing as described in this section.

Investigators shall counsel WOCBP and male subjects who are sexually active with WOCBP on the importance of pregnancy prevention and the implications of an unexpected pregnancy. Investigators shall advise WOCBP and male subjects who are sexually active with WOCBP on the use of highly effective methods of contraception. Highly effective methods of contraception have a failure rate of $< 1\%$ when used consistently and correctly.

At a minimum, subjects must agree to the use of two methods of contraception, with one method being highly effective and the other method being either highly effective or less effective as listed below:

HIGHLY EFFECTIVE METHODS OF CONTRACEPTION

- Progestogen only hormonal contraception associated with inhibition of ovulation.
- Hormonal methods of contraception including oral contraceptive pills containing combined estrogen + progesterone, vaginal ring, injectables, implants and intrauterine devices (IUDs) such as Mirena®
- Nonhormonal IUDs, such as ParaGard®
- Bilateral tubal occlusion
- Vasectomised partner with documented azoospermia 90 days after procedure

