 - ◆ Vasectomised partner is a highly effective birth control method provided that partner is the sole sexual partner of the WOCBP trial participant and that the vasectomised partner has received medical assessment of the surgical success.
- Intrauterine hormone-releasing system (IUS)
- Complete Abstinence
 - ◆ Complete abstinence is defined as the complete avoidance of heterosexual intercourse (refer to Glossary of Terms)
 - ◆ Complete abstinence is an acceptable form of contraception for all study drugs and must be used throughout the duration of the study treatment (plus the washout time of the investigational drug plus 30 days).
 - ◆ It is not necessary to use any other method of contraception when complete abstinence is elected.
 - ◆ Subjects who choose complete abstinence must continue to have pregnancy tests, as specified in [Section 6.4](#).
 - ◆ Acceptable alternate methods of highly effective contraception must be discussed in the event that the subject chooses to forego complete abstinence.
 - ◆ The reliability of sexual abstinence needs to be evaluated in relation to the duration of the clinical trial and the preferred and usual lifestyle of the subject.

LESS EFFECTIVE METHODS OF CONTRACEPTION

- Diaphragm with spermicide
 - Cervical cap with spermicide
 - Vaginal sponge with spermicide
 - Male or female condom with or without spermicide*
 - Progestogen-only oral hormonal contraception, where inhibition of ovulation is not the primary mode of action
- * A male and female condom must not be used together

UNACCEPTABLE METHODS OF CONTRACEPTION

- Periodic abstinence (calendar, symptothermal, post-ovulation methods)
- Withdrawal (coitus interruptus)
- Spermicide only
- Lactation amenorrhea method (LAM)

3.3.2 **Exclusion Criteria**

1. Target Disease Exceptions

- a) Subjects with non-secretory myeloma.
- b) Smoldering MM, defined as asymptomatic MM with absence of lytic bone lesions.
- c) Monoclonal Gammopathy of Undetermined Significance (MGUS) defined by all of the following: serum M protein < 3 g/dL, absence of lytic bone lesions, anemia, hypercalcemia and renal insufficiency related to monoclonal protein and (if determined) proportion of plasma cells in the bone marrow of 10% or less.
- d) Diagnosis of Waldenstrom's disease or other conditions in which IgM M protein is present in the absence of a clonal plasma cell infiltration with lytic bone lesions.

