4.3.2 Lenalidomide

Lenalidomide is an analogue of thalidomide. Thalidomide is a known human teratogen that causes severe life-threatening human birth defects. If lenalidomide is taken during pregnancy, it may cause birth defects or death to an unborn baby. Females should be advised to avoid pregnancy while taking lenalidomide (Revlimid®) and for up to 8 weeks after the last dose of lenalidomide. Furthermore, subjects taking lenalidomide should refrain from donating blood until at least 8 weeks or sperm until at least 116 days after last dose of lenalidomide.

Because of this potential toxicity and to avoid fetal exposure to lenalidomide, lenalidomide is only available under a special restricted distribution program. This program is called the Revlimid Risk Management Plan and provided from the sponsor separately for this study. Under this program, only prescribers and pharmacists registered with the program can prescribe and dispense the product. In addition, lenalidomide must only be dispensed to subjects who are registered and meet all the conditions of the Revlimid Risk Management Plan. Subjects who have the potential of pregnancy in the Revlimid Risk Management Plan must be instructed about contraception and undergo the scheduled pregnancy tests.

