Pregnancy Test	X		X*			X	X	For WOCBP only. Urine tests must have a sensitivity of at least 25 IU/L. Test must be completed on Day 1 and Day 15 within 24 hours prior to dosing. WOCBP must perform a pregnancy test 90 days off treatment. This test may be performed locally if the patient is unable to return to your center. *Not required in Cycles 19 and beyond. However, patients with irregular menstrual cycles must have a pregnancy test every two weeks.

Table 5.1-3: Long-term Procedural Outline (CA204116) Cycles 3 and Beyond

Procedure	Day 1	Day 8	Day 15	Day 22	Rest Day 23 - 28	End of Treatment	Days 30 & 60 Post End of Treatment ^a	Notes	
Efficacy Assessments									
Myeloma Urine and Serum Lab Tests	Every 4 weeks from date of the first dose of study drug until progression, regardless of whether patient is on study therapy or subsequent therapy.						
Day 1 of each cycle until disease progression.
 
24-hour urine sample can be collected within ± 7 days of visit, and must be obtained with each cycle in all subjects who have measurable UPEP M protein (≥ 200 mg/24 hours) at baseline.
 
Subjects without measurable urine M protein at baseline and at next two subsequent cycles do not have to submit q4 week urine samples with each cycle (but must submit q12 week urine samples) until SPEP M protein becomes undetectable. In order to full fill CR/sCR criteria, both serum and urine immunofixation must be performed and be negative on two consecutive assessment. Therefore, at the time SPEP becomes undetectable, UPEP sample collection must promptly resume for these subjects, and also continue q4 weeks until SPEP becomes detectable.
 
Central lab analysis. (Section 5.5.2)
		
Bone Marrow Aspiration/Biopsy	For confirmation of CR/sCR if applicable or, if clinically indicated at time of suspected disease progression						
Bone marrow aspirate is mandatory. Bone marrow biopsy is optional. Bone marrow samples must be assessed for clonal cells at the local lab by immunohistochemistry of the biopsy or immunofluorescence (flow cytometry) of the aspirate. Plasma cell percentage and light chain restriction assessments are required. (Section 5.5.2)
		

Table 5.1-3: Long-term Procedural Outline (CA204116) Cycles 3 and Beyond

Procedure	Day 1	Day 8	Day 15	Day 22	Rest Day 23 - 28	End of Treatment	Days 30 & 60 Post End of Treatment ^a	Notes
Lenalidomide Administration	Day 1 - 21 of each cycle							
Dexamethasone Administration	X	X	X	X				

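### Post-treatment pregnancy-prevention periods conflict in two places: 120 days against 8 weeks for women, and 180 against 120 days for men who rely on abstinence

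*Protocol*

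**What the plan says.** **Eligibility (Protocol 3.3.1).** Criterion 3(c) requires two contraceptive methods, for up to 120 days in women and up to 180 days in men after the last dose of study drug. Criterion 3(f) builds the women's figure from a 90-day washout and 30 further days, "for a total of 120 days post-treatment completion". Criterion 3(g), for men sexually active with women of childbearing potential, runs for treatment "plus the time to washout (90 days) plus 90 days (duration of sperm turnover) for a total of 180 days post-treatment completion". Criterion 3(b) reads: "Subjects must be willing to refrain from blood donations during study drug therapy and for 90 days after therapy".

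**Abstinence (same section, list of highly effective methods).** Abstinence "must be used throughout the duration of the study treatment (plus the washout time of the investigational drug plus 30 days"). The entry gives no separate period for men, and says that a subject who elects abstinence needs no other method.

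**Lenalidomide (Protocol 4.3.2).** "Females should be advised to avoid pregnancy while taking lenalidomide (Revlimid®) and for up to 8 weeks after the last dose of lenalidomide". Subjects are also to "refrain from donating blood until at least 8 weeks or sperm until at least 116 days after last dose of lenalidomide".

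**Pregnancy reporting (Protocol 6.4).** The exposure windows are again 120 and 180 days.

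Lenalidomide is listed as an investigational product in Section 4.1 and is given in both arms under Section 4.5.1. No passage says which period governs where they differ.

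**The concern.** Sections 3.3.1 and 4.3.2 both address what a woman should do after treatment, and they give different end dates. Section 4.3.2 is phrased as advice to be given to subjects, so a site could counsel from it alone. The abstinence entry has the same effect for men: read as complete in itself, it ends the precaution before 3(c), 3(g) and 6.4 do.

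What is at stake is subject safety. Section 4.3.2 itself links lenalidomide to thalidomide and to birth defects. Two sites relying on different sections could give the same kind of subject end dates about two months apart. The reporting window in 6.4 would then cover weeks in which a subject believed precautions were over.

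**Working it through.** **Inputs.** Washout 90 days (3(f), 3(g), 6.4); added 30 days for women and 90 days for men (same places); abstinence period of washout plus 30 days (3.3.1); 8 weeks for pregnancy avoidance and blood donation, and 116 days for sperm donation (4.3.2); 90 days for blood donation (3(b)).

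**The plan's own figures.** Women: 90 + 30 = 120 days. Men: 90 + 90 = 180 days. Both reproduce.

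**Conversions.** 8 weeks × 7 = 56 days. Abstinence: 90 + 30 = 120 days.

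| Comparison | Periods (days) | Difference | Can one period satisfy both passages as written? |
|---|---|---|---|
| Women: 3(c), 3(f), 6.4 against 4.3.2 | 120 and 56 | 120 − 56 = 64 | Different end dates for the same precaution |
| Men: 3(c), 3(g), 6.4 against abstinence entry | 180 and 120 | 180 − 120 = 60 | Different end dates for the same precaution |
| Women: 3(f) against abstinence entry | 120 and 120 | 120 − 120 = 0 | Agree |
| Blood donation: 3(b) against 4.3.2 | 90 and at least 56 | 90 − 56 = 34 | Yes: 90 days meets both |

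**The starting point for women.** Criterion 3(c) counts from the last dose of study drug; 4.3.2 counts from the last dose of lenalidomide. Let lenalidomide stop L days before the last study drug. Since lenalidomide is itself study drug, L cannot be negative. The 4.3.2 period then ends 56 − L days after the last study drug, so the gap is 120 − (56 − L) = 64 + L days.

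- All drugs stop together, L = 0: gap 64 days.
- Lenalidomide stops one 28-day cycle earlier (an illustration, not a figure from the plan): 64 + 28 = 92 days.
- L above 56: the 4.3.2 period ends while the subject is still on study treatment. Section 3.5 makes this possible, because subjects in the elotuzumab arm who must stop lenalidomide for the listed skin reactions or angioedema may continue elotuzumab and dexamethasone.

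**The case against.** **Different scope.** Section 4.3.2 concerns lenalidomide and sits under storage and dispensing, while 3(f) and 3(g) cover the combination. The duty to counsel on pregnancy prevention is in 3.3.1, and 4.3.2 sends contraception instruction to a separate risk management plan. This may explain how the two figures arose, and what subjects are actually told cannot be seen here. It does not remove the conflict. Criterion 3(c) applies to study drug in general, control subjects receive no elotuzumab yet face both figures, and neither passage refers to the other.

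**The abstinent man is outside 3(g).** That criterion covers men sexually active with women of childbearing potential, and a man who gives up abstinence must be offered another method. The entry may also have been drafted with women in mind, since it discusses pregnancy tests. The point about another method stands in part: a careful reader would keep him covered to day 180. But 3(c) covers men without that limit, and the exemption in 3(h) names azoospermic men and continuously inactive women, not abstinent men.

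**Stronger readings that a reader might infer, and why they fail.**

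- *The abstinence rule contradicts the periods for everyone.* For women it matches exactly.
- *Section 4.3.2 permits blood donation from 8 weeks and sperm donation from 116 days.* Both are minimum periods that a longer one satisfies. Sperm donation and contraception are also different precautions, so 116 against 180 days is not a contradiction.
- *The words* up to *make 8 weeks a ceiling.* Criterion 3(c) uses the same words for 120 and 180 days.
- *The last pregnancy test is too early.* Table 5.1-3 says "WOCBP must perform a pregnancy test 90 days off treatment", which is 120 − 90 = 30 days before the women's period ends. No passage requires testing to the end of contraception, so nothing is contradicted.
- *Most subjects are affected.* The documents give no sex split and no count of women of childbearing potential.

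A subject who follows the longest stated periods is never released before any passage allows.

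**Conclusion.** Two inconsistencies hold on the text. For women, 120 days stands against up to 56 days: a gap of 64 days if all drugs stop together and 64 + L if lenalidomide stops L days earlier. For men who elect abstinence as their sole method, 180 stands against 120 days, a gap of 60 days. The second figure assumes that the washout in the abstinence entry is the 90 days stated elsewhere in 3.3.1; the entry itself gives no number. Blood donation is a pair of unaligned figures, not a contradiction.

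This is an internal inconsistency of minor severity. It does not show that any subject was or will be released early, because the consent form and the lenalidomide risk management plan are not available here. It bears on subject safety wording only. No view is given on which period is right.

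**What to change.** The sponsor should reconcile 3.3.1 criteria 3(b), 3(c), 3(f) and 3(g), the abstinence entry, 4.3.2 and 6.4. One way is a single table of post-treatment periods by sex and by precaution (contraception or abstinence, pregnancy avoidance, blood donation, sperm donation), to which each of these places refers. The table should state which last dose starts each clock, including when lenalidomide stops before the other drugs, and should give men and women separate entries for abstinence. Those responsible for safety at the sponsor should confirm each figure, and the consent wording should be aligned with the result.

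The cost is a change to protocol and consent wording, with the review that goes with it. No visit, sample or analysis need be added.

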3.4 Concomitant Treatments

3.4.1 Required

Subjects must receive thrombo-embolic prophylaxis, per institutional guidelines or PI discretion. Examples of commonly used thrombo-embolic prophylaxis medications include aspirin, low molecular weight heparin, and vitamin K antagonists.

Subjects must receive pre-medications ([Sections 4.5.1.1](#) and [4.5.1.2](#)) prior to each dose of elotuzumab.

3.4.2 Permitted at Investigator's Discretion

- IV corticosteroids, diphenhydramine, or hydroxyzine, acetaminophen/paracetamol, H2 inhibitors (ie, cimetidine), leukotriene inhibitors (montelukast sodium) for the management of infusion reactions. Additional supportive measures should be provided as indicated including:
 - oxygen inhalation
 - epinephrine
 - bronchodilators
 - oral antiviral and antimicrobial prophylaxis
 - anti-emetics
 - and bisphosphonates.

Per the ASCO 2007 Clinical Practice Guidelines,³⁹ bisphosphonate therapy should be administered for a period of 2 years. At 2 years, the investigator should seriously consider discontinuing bisphosphonates in subjects with at least stable disease, although further use is at the discretion of the investigator.

Routine clinical practice for monitoring and prevention of osteonecrosis of the jaw (ie, comprehensive dental exam, treating active oral infections, eliminating sites of high risks for oral infection, excellent oral hygiene and avoiding invasive dental procedures while on treatment) must be followed.

- Erythropoietin (EPO) or darbepoetin (prior and ongoing use according to the package insert and institutional guidelines)
- Red blood cell or platelet transfusion
- Prophylactic administration of G-CSF in a subject who is experiencing recurrent difficulties with neutropenia, or therapeutic use in subjects with serious neutropenic complications (such as tissue infection, sepsis syndrome or fungal infection) may be considered at the investigator's discretion, consistent with American Society of Clinical Oncology guidelines (American Society of Clinical Oncology 2006).

3.4.3 Prohibited and/or Restricted Treatments

Any systemic, anti-myeloma therapy other than lenalidomide, dexamethasone and elotuzumab are prohibited while on study. Concomitant steroids, other than weekly dexamethasone ([Section 4.5.1](#)) or steroids allowed (as defined in eligibility criteria) are prohibited unless used to treat an adverse event. Guidelines for selection and use of other concomitant medications should be derived from the lenalidomide and dexamethasone prescribing information. Other than study medications, administration of any therapeutic or diagnostic investigational agent (for any indication) is prohibited while on study without prior Sponsor approval.

3.4.4 Surgery and Radiation

Use of radiotherapy or surgical intervention must be recorded on the Case Report Form.

Localized radiation therapy to a site of pre-existing disease may be permitted while on study. Following approval by the medical monitor, the patient may initiate or continue with protocol therapy without interruption during the course of palliative radiation therapy if the investigator believes that the risk of excessive bone marrow suppression or other toxicity is acceptable, and it is in the best interest of the patient to do so.

If the subject develops a definite increase in the size of existing bone lesions or soft tissue plasmacytomas that meets the criteria for disease progression, treatment must be discontinued for progressive disease regardless of whether radiation therapy is initiated.

Kyphoplasty, vertebroplasty or emergency orthopedic surgery is permitted.

3.5 Discontinuation of Subjects followings any Treatment with Study Drug

Subjects MUST discontinue investigational product (and non-investigational product at the discretion of the investigator) for any of the following reasons:

- Subject's request to stop study treatment
- Any clinical adverse event (AE), laboratory abnormality or intercurrent illness which, in the opinion of the investigator, indicates that continued participation in the study is not in the best interest of the subject
- Pregnancy (Subject must discontinue elotuzumab and lenalidomide).
- Termination of the study by Bristol-Myers Squibb (BMS)
- Loss of ability to freely provide consent through imprisonment or involuntarily incarceration for treatment of either a psychiatric or physical (eg, infectious disease) illness
- Progressive Disease (see [Section 5.5.4](#) for definition of disease progression).
- Subjects who receive any non-protocol specified systemic anti-myeloma therapy prior to documented progression will be discontinued from all study treatment (including lenalidomide/dexamethasone), however, tumor assessments must continue at 4 week intervals until documented progression.
- Subjects experiencing a Grade 4 infusion reaction must discontinue elotuzumab. Subjects may continue lenalidomide and dexamethasone treatment. Refer to [Section 4.5.2.2](#).

- Subjects experiencing angioedema, Grade 4 rash, exfoliative or bullous rash, Stevens Johnson syndrome, or toxic epidermal necrolysis related to lenalidomide must discontinue lenalidomide. Subjects in the elotuzumab arm may continue elotuzumab and dexamethasone.
- Subjects experiencing a 28-day delay in all study drugs lenalidomide, dexamethasone, and elotuzumab due to an adverse event(s) related to study treatment must be discontinued from study drug. Subjects experiencing delays unrelated to study therapy, for example due to radiation therapy may delay study treatment up to 42 days. Delays greater than 28 days must be discussed with the medical monitor.

In the case of pregnancy, the investigator must immediately notify the BMS Medical Monitor/designee of this event. In most cases, the study drug will be permanently discontinued in an appropriate manner. If the investigator determines a possible favorable benefit/risk ratio that warrants continuation of study drug, a discussion between the investigator and the BMS Medical Monitor/designee must occur.

All subjects who discontinue study drug should comply with protocol specified follow-up procedures as outlined in [Section 5](#). The only exception to this requirement is when a subject withdraws consent for all study procedures including post-treatment study follow-up or loses the ability to consent freely (ie, is imprisoned or involuntarily incarcerated for the treatment of either a psychiatric or physical illness).

If study drug is discontinued prior to the subject's completion of the study, the reason for the discontinuation must be documented in the subject's medical records and entered on the appropriate case report form (CRF) page.

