4 STUDY DRUG

Study drug includes both Investigational [Medicinal] Product (IP/IMP) and Non-investigational [Medicinal] Products (Non-IP/Non-IMP) and can consist of the following:

- All products, active or placebo, being tested or used as a comparator in a clinical trial.
- Study required premedication, and
- Other drugs administered as part of the study that are critical to claims of efficacy (eg, background therapy, rescue medications)
- Diagnostic agents: (such as glucose for glucose challenge) given as part of the protocol requirements must also be included in the dosing data collection.

All protocol-specified investigational product and non- investigational products are considered study drug. See [Table 4-1](#) for product description of elotuzumab, lenalidomide and dexamethasone.

Table 4-1: Study Drugs for CA204116 Treatment Period

Product Description / Class and Dosage Form	Potency	IP/Non-IMP	Blinded or Open Label	Packaging/ Appearance	Storage Conditions (per label)
Elotuzumab Powder for Solution for Infusion	400 mg/vial	IP	Open Label	20 mL Vial/ Sterile, white to off-white, preservative-free, lyophilized cake	Store at 2° - 8 °C
Lenalidomide (Revlimid®)capsule	5 mg, 10 mg, 15 mg and 25 mg	IP	Open Label	21 capsules per bottle	Store at 15° - 25°C.
Dexamethasone Tablets	2 mg and 4 mg & various strengths	Non-IMP	NA	Various	Refer to label on container or package insert/summary of product characteristics
Dexamethasone Solution	4 mg/mL, 8 mg/mL & various strengths	Non-IMP	NA	Various	Refer to label on container or package insert/summary of product characteristics

Elotuzumab and lenalidomide will be supplied by the BMS. Dexamethasone tablets and solution for IV infusion will be obtained by the investigating site's standard prescribing procedures.

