4.1 Investigational Product

An investigational product, also known as investigational medicinal product in some regions, is defined a pharmaceutical form of an active substance or placebo being tested or used as a reference in a clinical study, including products already with a marketing authorization but used or assembled (formulated or packaged) differently than the authorized form, or used for an unauthorized indication, or when used to gain further information about the authorized form.

The investigational product should be stored in a secure area according to local regulations. It is the responsibility of the investigator to ensure that investigational product is only dispensed to study subjects. The investigational product must be dispensed only from official study sites by authorized personnel according to local regulations.

In this protocol, investigational product(s) is/are: Elotuzumab powder for solution for infusion, lenalidomide (Revlimid®) capsules 5 mg, 10 mg, 15 mg, and 25 mg.

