6.4 Pregnancy

If, following initiation of the study drug, it is subsequently discovered that a study subject or a female partner of a male study participant is pregnant or may have been pregnant at the time of study exposure, including during the time to washout (90 days) plus one ovulatory cycle (30 days) for a total of 120 days; or plus one spermatogenesis cycle (90 days) for a total of 180 days after product administration, the investigator must immediately notify the BMS Medical Monitor/designee of this event and complete and forward a Pregnancy Surveillance Form to BMS Designee within 24 hours and in accordance with SAE reporting procedures described in [Section 6.1.1](#).

In most cases, the study drug will be permanently discontinued in an appropriate manner (eg, dose tapering if necessary for subject safety).

In the rare event that the benefit of continuing study drug is thought to outweigh the risk, after consultation with BMS, the pregnant subject may continue study drug after a thorough discussion of benefits and risk with the subject

Protocol-required procedures for study discontinuation and follow-up must be performed on the subject unless contraindicated by pregnancy (eg, x-ray studies). Other appropriate pregnancy follow-up procedures should be considered if indicated.

The investigator must immediately notify the BMS (or designee) Medical Monitor of this event and complete and forward a Pregnancy Surveillance Form to BMS (or designee) within 24 hours and in accordance with SAE reporting procedures described in [Section 6.1.1](#).

Follow-up information regarding the course of the pregnancy, including perinatal and neonatal outcome and, where applicable, offspring information must be reported on the Pregnancy Surveillance Form.

Any pregnancy that occurs in a female partner of a male study participant should be reported to BMS. Information on this pregnancy will be collected on the Pregnancy Surveillance Form.

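### Protocol Section 6.4, read literally, lets a pregnant subject continue elotuzumab or lenalidomide, which Section 3.5 says must stop

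*Protocol*

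**What the plan says.** Protocol Section 3.5 opens with a general rule: "Subjects MUST discontinue investigational product (and non-investigational product at the discretion of the investigator) for any of the following reasons". One of the listed reasons is "Pregnancy (Subject must discontinue elotuzumab and lenalidomide". Neither the rule nor the bullet carries an exception for those two drugs.

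The closing paragraph of the same section returns to pregnancy. After requiring immediate notification of the Medical Monitor, it says: "In most cases, the study drug will be permanently discontinued in an appropriate manner". It then adds: "If the investigator determines a possible favorable benefit/risk ratio that warrants continuation of study drug", and in that case requires a discussion between the investigator and the Medical Monitor.

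Section 6.4 (Pregnancy) goes further. For a rare situation in which benefit is judged to exceed risk and the sponsor has been consulted, it states that "the pregnant subject may continue study drug after a thorough discussion of benefits and risk with the subject".

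The term is defined in Section 4: "All protocol-specified investigational product and non- investigational products are considered study drug". Section 4.1 identifies the investigational products: "In this protocol, investigational product(s) is/are: Elotuzumab powder for solution for infusion, lenalidomide". Section 4.2 lists the non-investigational products: dexamethasone, H1 and H2 blockers, acetaminophen and thrombo-embolic prophylaxis.

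**The concern.** The protocol gives two answers to the same safety question. A site working from the pregnancy bullet in Section 3.5 would stop both drugs. A site working from Section 6.4, the section titled for pregnancy, would find that study drug may continue in a rare case. It would find neither the bar nor a cross-reference to Section 3.5.

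At stake is fetal exposure to a drug that Section 4.3.2 calls an analogue of a known human teratogen and links to birth defects or fetal death. Elotuzumab is affected too. In the text available, the Section 3.5 lead-in and bullet are the only places that require elotuzumab to stop in pregnancy without exception, and the closing paragraph of the same section blurs that requirement.

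**Working it through.** No arithmetic applies; the check is to set the passages side by side and apply the protocol's own definitions.

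| Place in the protocol | Elotuzumab and lenalidomide | Non-investigational product |
|---|---|---|
| 3.5 lead-in and pregnancy bullet | Must stop; no exception | Investigator's discretion |
| 3.5 closing paragraph | Study drug stops in most cases; continuation is a matter for discussion; no drug named | Same wording; no drug named |
| 6.4 | Study drug may continue in a rare case after sponsor consultation; no drug named | Same wording; no drug named |

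1. **Does study drug include the barred drugs?** Yes. Section 4 covers all investigational and non-investigational products, and Section 4.1 names elotuzumab and lenalidomide as the investigational ones. Both are barred in the ELd arm; in the Ld arm only lenalidomide applies.

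2. **Does either continuation passage narrow the term?** No. Neither names a drug or refers back to the bullet.

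3. **Do the two continuation passages carry equal weight?** No. The closing paragraph of Section 3.5 requires a discussion and does not itself grant permission. Only Section 6.4 says that the subject may continue. The direct contradiction is therefore between the Section 3.5 bar and Section 6.4; the closing paragraph adds ambiguity inside Section 3.5.

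4. **Does the protocol name drugs when it means only some of them?** Yes, in Section 3.5 itself. After a Grade 4 infusion reaction, elotuzumab stops and the subject may stay on lenalidomide and dexamethasone. After severe lenalidomide-related rash, lenalidomide stops and an ELd subject may stay on elotuzumab and dexamethasone. For pregnancy, the text on continuing names none.

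5. **Is the default clear for the remaining products?** No. Under the Section 4 definition, permanently stopping study drug would also cover dexamethasone and prophylaxis, which the Section 3.5 lead-in leaves to the investigator.

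6. **What other safeguards exist?**
   - Section 3.3.1 requires two contraceptive methods (complete abstinence suffices alone), and negative pregnancy tests before study drug starts in women of childbearing potential. A lenalidomide prescription must wait until the prescriber has verified the negative tests. This last rule is an entry criterion, so its reach to later cycles is arguable.
   - Tables 5.1-2 and 5.1-3 require weekly tests in Cycles 1 and 2, then tests on Day 1 and Day 15. From Cycle 19 the Day 15 test is dropped, except that women with irregular menstrual cycles are tested every two weeks.
   - Section 4.3.2 and both tables tie lenalidomide dispensing to the Revlimid Risk Management Plan.

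   These controls lower the chance of exposure. The contraception and testing rules apply to elotuzumab as well as lenalidomide. None of them, in the text available, says which drugs may continue once a pregnancy is confirmed. The Plan is a separate document, and whether it bars dispensing in pregnancy cannot be checked here.

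**The case against.** The best defence is that a specific mandatory rule governs a general one. Section 3.5 uses capitals and names two drugs; the continuation passages are generic. Because the lead-in leaves non-investigational product to the investigator, the exception would still have something to act on. On that reading nothing conflicts. Harm would also require the investigator and the sponsor together to set aside an explicit requirement, after discussing the risks with the subject, for a drug that the protocol itself describes as dangerous in pregnancy.

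Much of this stands. It shows that the contradiction is unlikely to be acted on, and it is a sensible guess at what was intended. It does not remove the contradiction, because the reader must override a written definition to reach the harmless meaning, and nothing in Section 6.4 points that way.

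Three stronger readings are tempting, and the documents do not support them:

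- **The protocol deliberately authorises lenalidomide or elotuzumab in pregnancy.** The Section 3.5 bullet says the opposite. What exists is an unrestricted general term beside a specific bar.
- **Elotuzumab has no pregnancy safeguards.** Pregnancy tests are required before any study drug starts and through treatment, and the contraception rule names elotuzumab.
- **The exception can only mean dexamethasone.** Section 4.2 lists other non-investigational products, including heparin prophylaxis. Section 4.5.3 does not supply a dexamethasone-only meaning either: its statement about a subject continuing on a single drug concerns lenalidomide.

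**Conclusion.** The point holds as a contradictory safety instruction: Section 6.4 taken literally permits what Section 3.5 forbids, and the closing paragraph of Section 3.5 leaves the same question open. It should be corrected.

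The expected frequency is low. About 80 subjects are randomized, each aged 65 or older or with a comorbidity that prevents transplant, and contraception is required. The documents give no expected number of pregnancies, so no rate can be stated. The possible harm per event is severe. No endpoint, sample size, error rate or analysis is affected.

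The conclusion rests on the Section 4 definition applying wherever the protocol says study drug. It also rests on the text available, which does not include the Revlimid Risk Management Plan or Appendix 3. If the Plan bars dispensing to a pregnant subject, the lenalidomide risk shrinks further, but the protocol's wording would still conflict.

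**What to change.** In Section 6.4 and in the last paragraph of Section 3.5, replace the open continuation wording with:

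> Elotuzumab and lenalidomide must be permanently discontinued in a pregnant subject, with no exception. Continuation of non-investigational product (e.g. dexamethasone, thrombo-embolic prophylaxis) is at the investigator's discretion per Section 3.5, after discussion with the Medical Monitor.

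Referring to non-investigational product rather than to dexamethasone alone avoids barring heparin or other prophylaxis by accident.

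The cost is two sentences in two places, with no statistical consequence. Any sponsor-approved exception for elotuzumab or lenalidomide disappears, but Section 3.5 already excludes one. The one added step is a Medical Monitor discussion before non-investigational product continues. The burden is small, since both sections already require the Medical Monitor to be told of a pregnancy immediately.
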